***Laboratory sample collection before and during the controlled fasting challenge***

On the morning of inpatient visit for the controlled fasting challenge, after vital signs and other non-interventional assessments have been performed, samples will be collected for standard clinical chemistry (including lipid levels), hematology, coagulation panel, and urinalysis. These samples should be collected at least 2 to 4 hours after the subject's last meal prior to admission and sent to the central lab. A sample for STAT AST and ALT level analysis will also be collected at this time and sent to the local laboratory; the Investigator or delegated subinvestigator should review the results before starting the controlled fasting challenge.

All subjects should have a morning cortisol and ACTH measurement prior to their baseline fasting challenge. Cortisol and ACTH results should be reviewed by the Investigator or delegate before starting the fasting challenge. Abnormal morning cortisol results might require postponing the fasting challenge until further HPA axis testing is performed.

For subjects with suspected HPA axis dysfunction (eg, after prolonged steroid treatment) supplemental tests can be conducted (eg, stimulation tests) before deciding if it is safe to conduct the fasting challenge. In most cases, morning cortisol and supplemental tests will be conducted one week prior to the visit. It is also possible to perform these tests at the site on Day 1 of the visit under the conditions that all results will be available prior to the beginning of the CFC.

Total urine voided over the 24-hour period starting at the time of inpatient admission will be collected during the controlled fasting challenge.

Blood samples for measurement of cortisol, ACTH, free fatty acids, glucagon, insulin, C-peptide, growth hormone, IGFBP1, alanine and ketone levels (3-hydroxy butyrate) will be collected at the beginning (ie, immediately after the post-dinner dose of cornstarch, or immediately after dinner for subjects who do not take a post-dinner dose of cornstarch) and end of the controlled fasting challenge, or more frequently at the Investigator's discretion. A final sample for glucose, lactate, growth hormone, IGFBP1, ACTH and cortisol measurement will be collected 30 minutes after the end of the controlled fasting challenge. Samples should be prepared and transported to the local laboratory in accordance with the site's standard procedures.

Blood samples for STAT analysis of glucose and lactate will be collected through an indwelling catheter (central or peripheral) at the following time points:

- At the beginning of the fast (ie, immediately after the post-dinner dose of cornstarch, or immediately after dinner for subjects who do not take a post-dinner dose of cornstarch)
- Approximately every 60 minutes ( $\pm$  5 minutes) until the glucose level decreases to  $\leq$  70 mg/dL ( $\leq$  3.9 mmol/L)

- Approximately every 30 minutes ( $\pm$  5 minutes) until the glucose level decreases to  $< 54$  mg/dL ( $< 3.0$  mmol/L) or when the subjects experience signs and symptoms of hypoglycemia, or when the fast reaches 15 hours without hypoglycemia, whichever occurs first

Samples should be prepared and transported to the local laboratory in accordance with the site's standard procedures. To ensure the safety of the study subjects, results from these tests should be available within 30 minutes after the blood sample collection. Capillary glucose will be performed at the same time points as blood samples for STAT analysis of glucose and lactate. Results of the capillary glucose and readings from CGM at corresponding time points will be noted on a controlled fasting challenge results sheet.

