#### **8.1.1. Symptom-Free Euglycemia (Controlled Fasting Challenge)**

The subject's ability to maintain symptom-free euglycemia during a controlled fasting challenge will be assessed at time points specified in the Schedule of Events. However, if clinically indicated, the controlled fasting challenge can also be performed at an unscheduled visit.

The controlled fasting challenge requires a 24-hour inpatient stay in a hospital or research facility and will be performed after all other study visit assessments (except [REDACTED]) have been completed and the required laboratory assessments (as specified below) have been reviewed by the Investigator (or a subinvestigator assigned to review results and make clinical decisions per the site delegation log). Subjects should wear their CGM device throughout the fasting challenge, and should not change the sensor prior to the assessment.

If a subject is suspected to have HPA axis impairment (eg, due to prolonged steroid treatment; may be confirmed by morning cortisol or stimulation tests), the fasting challenge may have to be rescheduled to a later date in order to ensure subject safety and provide interpretable results.

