Before the controlled fasting challenge begins, the study site will provide dinner for the subject. The dinner meal will be personalized for each subject, and will include a target carbohydrate range and overall composition in protein, fats and dietary fibers that is as close as possible to the subject's most current dinner prescription, but not higher in carbohydrate content than the dinner consumed at their baseline fasting challenge. The start and stop time of the dinner meal and its full dietary composition including amount of carbohydrates consumed will be recorded. After dinner, subjects will be given an oral dose of cornstarch equivalent per their most recent cornstarch prescription, at approximately the same time that they typically take it, but no later than 3 hours post dinner. The amount of cornstarch administered should not be higher than that consumed by the subject at the baseline fasting challenge. The time of ingestion of prefasting cornstarch and the amount consumed will be recorded. After the cornstarch is ingested, the controlled fasting challenge will begin, and the start time will be recorded accordingly. If a subject does not receive cornstarch before going to bed at the time of the CFC, the fasting challenge will start after they complete their dinner. Subjects will be instructed to minimize activity after they finish eating dinner until the end of the controlled fasting challenge.

During the fast, subjects may not ingest any food or drink other than water. The controlled fasting challenge will end when the subject's glucose level decreases to  $< 54$  mg/dL ( $< 3.0$  mmol/L) or when the subjects experience signs and symptoms of hypoglycemia, or when the fast reaches 15 hours without hypoglycemia, whichever occurs first. The stop time of the controlled fasting challenge will be recorded. At the end of the controlled fasting challenge, the subject's hypoglycemia should be treated per the institution's standard procedure, which may include providing the subject with a meal, cornstarch, or IV glucose, if medically indicated.

In cases where the controlled fasting challenge is terminated prematurely before the subject reaches a glucose level of < 54mg/dL or without the subject experiencing signs and symptoms of hypoglycemia, or due to any deviation in the fasting challenge protocol, an ad hoc fasting challenge may be scheduled within 6 weeks from the scheduled fasting challenge.

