### **10.2.3. Efficacy Analyses**

#### **10.2.3.1. Symptom-Free Euglycemia**

The time (in minutes) to the first hypoglycemic event (defined as glucose  $< 54$  mg/dL [ $< 3.0$  mmol/L]) during a controlled fasting challenge will be determined for all subjects at Day 0 and Weeks 12, 24, and 52. Full details of the analysis will be provided in the SAP.

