- aa Blood samples for measurement of glucose and lactate (venous) levels will be collected at the beginning of the controlled fasting challenge, then approximately every 60 minutes ( $\pm 5$  minutes) until the glucose level decreases to  $\leq 70$  mg/dL ( $\leq 3.9$  mmol/L), then approximately every 30 minutes ( $\pm 5$  minutes) until the glucose level decreases to  $< 54$  mg/dL ( $< 3.0$  mmol/L) or the fast reaches 15 hours without hypoglycemia, whichever occurs first. Samples should be sent to the local laboratory (STAT sample) and results should be available within 30 minutes or less of blood sample collection for the safety of the subject.
- bb Subjects will be registered in the IWRS at Screening and after eligibility for enrollment is confirmed.
- cc The site will schedule the dosing visit in the IWRS no less than 3 days before, preferably 7 days before, the DTX401 infusion to allow time for DTX401 to be shipped and delivered to the site.
- dd If the subject continues to be on steroid regimen and the Investigator determines that it is not safe to proceed with the CFC, the Week 12 visit may become an outpatient visit. Investigators should try to complete an adhoc CFC assessment as soon as the subject has completed steroid treatment and within 8 weeks of the Week 12 visit, as an unscheduled visit.

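### No laboratory or capillary glucose is explicitly required when a fasting challenge stops for symptoms, so such stops can enter the sole secondary endpoint without biochemical verification

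*Protocol*

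**What the plan says.** Protocol 8.1.1 ends a challenge at glucose below 54 mg/dL "or when the subjects experience signs and symptoms of hypoglycemia, or when the fast reaches 15 hours without hypoglycemia, whichever occurs first". Symptoms alone are therefore enough to stop.

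Two separate sets of blood samples surround the stop.

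- **End-of-challenge panel (8.1.1).** Sampled as the fast starts and again as it stops: "Blood samples for measurement of cortisol, ACTH, free fatty acids, glucagon, insulin, C-peptide, growth hormone, IGFBP1, alanine and ketone levels (3-hydroxy butyrate) will be collected". Glucose and lactate are not listed. Section 8.2.6.4 and Table 6 footnote m repeat the list without them. A further sample follows: "A final sample for glucose, lactate, growth hormone, IGFBP1, ACTH and cortisol measurement will be collected 30 minutes after the end".
- **STAT glucose and lactate (8.1.1).** "Blood samples for STAT analysis of glucose and lactate will be collected through an indwelling catheter (central or peripheral) at the following time points". These are once when the fast starts, about every 60 (±5) minutes until glucose is 70 mg/dL or less, then about every 30 (±5) minutes until glucose is below 54 mg/dL, symptoms occur, or 15 hours pass. Table 6 footnote aa gives the same grid but ends it only at glucose below 54 mg/dL "or the fast reaches 15 hours without hypoglycemia, whichever occurs first". Symptoms are not mentioned there.

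Other glucose sources depend on the grid or are supplemental. "Capillary glucose will be performed at the same time points as blood samples for STAT analysis of glucose and lactate". CGM readings are noted on the results sheet at the corresponding times, and "Subjects should wear their CGM device throughout the fasting challenge, and should not change the sensor prior to the assessment".

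For the endpoint, Protocol Sections 2 and 10.2.3.1 define the event as glucose below 54 mg/dL. The time to it "during a controlled fasting challenge will be determined for all subjects at Day 0 and Weeks 12, 24, and 52". SAP 8.5.1 defines the event as glucose below 60 mg/dL. It adds that if a challenge is stopped for a symptomatic hypoglycemic event, or an intervention is given, the event time is the time of termination. SAP Section 9 lists no changes from the protocol.

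**The concern.** The endpoint in the protocol is biochemical, but one of the three ways to end a challenge is not. Symptoms are partly subjective and the study is open-label. If a subject stops for symptoms between two grid points, no sentence clearly requires a glucose value at the stop. The sample drawn 30 minutes later cannot stand in for it, because Protocol 8.1.1 allows a meal, cornstarch or IV glucose once the challenge ends.

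Two uses of the data suffer. First, a symptom stop at a true glucose of 75 mg/dL and one at 50 mg/dL would receive the same treatment in SAP 8.5.1, and no planned summary separates them. Second, Protocol 1.3.1 and 3.1 attribute short fasts that are hard to interpret to high insulin and a slow cortisol response to hypoglycemia. Reading the end-of-challenge insulin and cortisol that way needs the glucose at the same moment. The same sections justify 54 mg/dL on the ground that symptoms may not appear until about that level. A glucose at each symptom stop is the direct check of that premise.

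**Working it through.** The plan gives no figure to reproduce. The check is a side-by-side reading of the passages plus interval arithmetic on the sampling grid.

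**1. Is a glucose tied to each type of stop?**

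| Reason for stop | Glucose at the stop under the written schedule |
|---|---|
| Glucose below 54 mg/dL | Yes: a glucose result is itself the trigger |
| 15 hours reached | Yes, nominally: 15 × 60 = 900 min, a multiple of both 60 and 30 |
| Symptoms between grid points | Not explicitly: absent from the end panel, and the grid names no draw there |

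The gap is confined to the third row, and to any intervention given between grid points.

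**2. How old can the last scheduled value be?** Maximum age = nominal interval + late tolerance on the next draw + early tolerance on the last draw.

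- 60-minute grid (glucose above 70 mg/dL): 60 nominal; 60 + 5 + 5 = 70 min at the extremes.
- 30-minute grid (70 mg/dL or less): 30 nominal; 30 + 5 + 5 = 40 min at the extremes.

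**3. How far apart are the two values that bracket the stop?** Add the 30 minutes to the final sample.

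- 60-minute grid: 60 + 30 = 90 min nominal; 70 + 30 = 100 min at the extremes.
- 30-minute grid: 30 + 30 = 60 min nominal; 40 + 30 = 70 min at the extremes.

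**4. Can that gap change the classification?** The documents give no rate of fall, so I assume 10 to 20 mg/dL per hour for illustration.

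- Last value 71 mg/dL, stop just under 60 min later: 71 − 10 = 61, or 71 − 20 = 51 mg/dL.
- Last value 60 mg/dL, stop just under 30 min later: 60 − 5 = 55, or 60 − 10 = 50 mg/dL.

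Each pair falls on both sides of 54 mg/dL. The first also straddles the 60 mg/dL used in SAP 8.5.1.

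**5. What does the analysis do with such a stop?** SAP 8.5.1 needs only the stop time, which Protocol 8.1.1 requires to be recorded. The subject gets an event at that time whatever the glucose. With 3 subjects per cohort, any error in one subject's time moves the cohort mean by one third of that error.

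**6. Which threshold applies?** At 18.016 mg/dL per mmol/L, 54 mg/dL is 3.00 mmol/L and 60 mg/dL is 3.33 mmol/L. The protocol uses 54 mg/dL with 3.0 mmol/L, SAP 4.2 pairs 54 mg/dL with 3.3 mmol/L, and SAP 8.5.1 uses 60 mg/dL with 3.3 mmol/L.

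**The case against.** A reader might infer that no glucose is drawn at a symptom stop. The documents do not support that. Glucose and lactate are missing from the end panel because Protocol 8.1.1 schedules them separately. The last item of that schedule names symptom onset under a heading about sampling times, so it can be read as including a draw there, with a paired capillary test. Section 8.2.6.1 also allows a laboratory test to be repeated on any concern. What stands is that the wording is ambiguous: the schedule orders a draw at the beginning of the fast but has no matching item for the end, and footnote aa does not mention symptoms.

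A reader might also infer that a symptom stop cannot be classified. That is wrong for the planned analysis, because SAP 8.5.1 assigns it an event at termination. The rule also suits an objective of symptom-free euglycemia, which a symptomatic subject has not met. The missing piece is verification against the glucose definition.

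CGM is the best counter-argument. The device is worn throughout the fast, and the 5-minute term in SAP 8.5.3 suggests frequent readings, so a near-simultaneous value may often exist. But Protocol 8.1.2 calls these data supplemental, SAP 8.5.3 limits them to Cohorts 3 and 4, and the challenge listing in SAP 8.5.1 names laboratory values and capillary glucose (if available), not CGM.

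Finally, the size is uncertain. The documents do not say how often challenges stop for symptoms. The 70-minute gap needs both tolerances at their extremes and symptoms before any reading of 70 mg/dL or less. On the protocol's premise that symptoms come late, most symptom stops would fall on the 30-minute grid. The endpoint is summarized descriptively in about 12 subjects, and no test or decision rule is shown to change. All of this stands, and it makes the point an inexpensive improvement, not a fatal flaw.

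**Conclusion.** The point holds in this form: the protocol does not explicitly require a laboratory or capillary glucose at a symptom stop. The last scheduled value may be up to about 40 minutes old, or 70 minutes on the sparser grid at the extremes. SAP 8.5.1 then counts the stop as an event with no glucose condition, although the protocol defines the endpoint by glucose below 54 mg/dL only. Such stops can therefore enter the sole secondary endpoint without biochemical verification, and nothing planned shows how many they are.

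This rests on reading the STAT schedule as not ordering a draw at symptom onset. If sites read it the other way, the values exist and only the wording and the reporting need attention. The assumed fall of 10 to 20 mg/dL per hour shows that the gap could matter. It does not estimate how often it did.

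**What to change.** **Protocol.** In 8.1.1, 8.2.6.4 and Table 6 footnotes m and aa, add STAT glucose and lactate, with a paired capillary reading, to the blood already drawn at the end of the challenge, for every type of stop. Reconcile footnote aa with 8.1.1 on whether symptoms end the sampling.

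**SAP 8.5.1.** Keep the termination-time rule, but report symptom and intervention stops separately by glucose at the stop: below threshold, at or above threshold, or not available. Reconcile the below-54 and below-60 mg/dL definitions, and the mmol/L value in SAP 4.2, with the protocol endpoint. State any intended departure in SAP Section 9.

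**Cost.** Two extra analytes and one capillary test per challenge, and one more descriptive summary. No visit is added, and nothing changes in when a challenge stops or how the subject is treated. The sampling change helps only challenges still to come. SAP 3.7 reports safety review to Week 52 for Cohorts 1 to 3 and Week 24 for Cohort 4, so few may remain. The SAP change can be applied to every challenge already done, with the not-available category showing the extent of the gap.

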### **8.1.2. Continuous Glucose Monitoring**

Supplemental information on glucose level trends will be collected using a continuous glucose monitoring (CGM) device. The site will provide a CGM device to the subject during the Screening Period after determining that the subject is eligible for the study (Table 6). Subjects will be educated on the appropriate care and use of the CGM device and sensors, and instructed to wear the CGM device through the Week 52 visit or early withdrawal. Data from the subject's CGM device will be transferred to the Sponsor throughout the study, including a final data transfer at the end of the Week 52 visit or early withdrawal. Details regarding the care and use of the CGM device and sensors and data transfer to the Sponsor are provided in the Manual of Operations.

### **8.1.3. Morning Glucose Levels**

If a subject is unable to use the assigned CGM, the subject should collect morning glucose levels at least 2 mornings per week throughout the study (Table 6). Subjects should adhere to their prescribed overnight cornstarch diet. Morning glucose levels should be measured using the subject's own glucose monitoring device before taking their morning dose of cornstarch. The collection date, collection time, glucose level, and prior day's overnight cornstarch dose taken should be collected on the Morning Glucose Level monitoring worksheet provided by the site. Subjects will be instructed to bring the completed worksheets to each study visit. Data collected on the worksheet will be captured on the appropriate page of the eCRF.

### **8.1.4.**

[REDACTED]

[REDACTED]

**8.1.5.**

Subjects will be asked to complete the following [REDACTED]:

- [REDACTED]
- [REDACTED]
- [REDACTED]
- [REDACTED]
- [REDACTED]
- [REDACTED]
- [REDACTED]
- [REDACTED]

[REDACTED]

[REDACTED]

[REDACTED]

**8.1.6. Endpoint Outcomes Interviews**

Up to two 30-minute scripted telephone interviews will be conducted during the Week 24 and 52 study visits to better quantify the subject experience in the study. The interviews will be conducted by a third-party vendor, Endpoint Outcomes, specializing in the capture of caregiver and subject-reported data. Endpoint Outcome uses a script as an interview guide to serve as a basis for the discussion. The interview will be conducted by phone.

The subject has consented to the interview per the study's main ICF. However, prior to the start for the interview, Endpoint Outcomes will verbally ask for the subject's consent for the interview to be audio-recorded. With the subject's verbal consent, the interview will be audio-recorded, and the interviewer will proceed through a script. If the subject does not give permission for the session to be audio-recorded, the interview will not proceed. Subjects will be asked about their experience in the study. They may refuse to answer any question in the interview and may stop at any time.

Site staff will facilitate the phone call so that the subject's contact information remains anonymous. Personal information (including subject's name and telephone number) will remain anonymous and will not be provided to the Sponsor or Endpoint Outcomes. Subjects will be identified only by their study specific subject IDs.

All digital recordings will be stored by Endpoint Outcomes in a secure place where only Endpoints Outcome personnel directly related to this study will be able to access it. The audio interviews will be transcribed by a transcription company under contract and a confidentiality agreement, who will provide the written transcripts that will be further analyzed by Endpoint Outcomes. The transcription company is also contracted to ensure that transcripts will not contain any personal identifying information (eg, reference of first names) that may have been revealed during the interview process; personal identifying information will be removed and will not appear in the final transcript. Data from the interview will be shared with the Sponsor only after all identifying information has been removed.

## **8.2. Safety Assessments**

Planned time points for all safety assessments are listed in the Schedule of Events ([Table 6](#)).

Safety will be assessed based on AEs, SAEs, vital sign measurements, complete and targeted physical examination findings, ECG results, documented symptomatic hypoglycemic events, clinical laboratory assessments (clinical chemistry [including liver function tests], hematology, coagulation panel, and urinalysis), vector shedding, vector genome determination, measurement of neutralizing antibody titer to AAV8, measurement of AAV8 binding antibody immunoglobulin G (IgG), assessment of any cell-mediated immune responses to AAV8 and G6Pase, and measurement of anti-G6Pase antibodies.

### **8.2.1. Vital Sign Measurements**

Vital sign measurements will be made at the time points specified in the Schedule of Events ([Table 6](#)). During the study, vital sign measurements are to be collected before any stimulating or anxiety-provoking procedures (eg, phlebotomy). Vital sign measurements will include heart rate, blood pressure (systolic and diastolic), and respiratory rate. Height (at the Screening visit only) and weight will also be recorded.

- On Day 0, weight will be measured to ensure that the weight is within 10% of the screening weight used to calculate the dose of DTX401. Subjects with a confirmed change in weight that is > 10% from Screening should be further evaluated to exclude the presence of an acute condition or illness. If a benign explanation for the weight

change is identified and documented, DTX401 can be given and dosed using the weight obtained on Day 0.

- Vital signs should be measured with the subject having rested for at least 5 minutes beforehand. It is preferred that the measurement be late with the subject rested, rather than on time with the subject not sufficiently rested. If the subject is not sufficiently rested, this needs to be stated in the source documents.
- On Day 1, vital signs will be measured at predose, approximately 5 minutes, and 0.5 ( $\pm$  5 minutes), 1 ( $\pm$  5 minutes), 4 and 8 hours ( $\pm$  15 minutes) after the start of DTX401 infusion. Vital signs will also be measured approximately 22 hours ( $\pm$  1 hour) after the start of infusion, prior to subject discharge.
- It is acceptable for heart rate to be captured from the 12-lead ECG (Section 8.2.3).

Vital sign measurements will be recorded on the appropriate page of the eCRF. The medical monitor should be notified of any clinically significant changes or abnormal value in vital sign measurements (Section 9.1.2). If, in the medical and scientific judgment of the Investigator, a clinically significant change or abnormal vital sign measurement is observed, it should be recorded as an AE or SAE, as defined in Section 9.1.2, on the appropriate pages of the eCRF.

